2.1 Design

An efficacy study in Caucasian subjects by Evstatiev et al, 2011 [15] demonstrated that FCM administered using a simplified dosing formula (as proposed in this study) was superior to IS dosed using the Ganzoni formula (at multiple 200 mg iron doses). However, since no data are available on the use of FCM in Chinese patients, a non-inferiority design has been chosen for this study, assuming that FCM treatment is at least as good as IS in Chinese subjects. A randomised design was chosen to reduce bias in baseline differences between the treatment groups.

Due to the differences in posology between the study drug (FCM) and the comparator (IS) additional administrations may be required for subjects receiving IS. In a 65 kg subject with Hb of 9 g/dL at screening, FCM would require 2 individual doses of FCM (1,000 mg iron followed by a single dose of 500 mg iron 1 week later). However, if the same subject was randomised to receive IS, the cumulative dose required (as per label) would be 1,436 mg iron which would require 7 individual 200 mg iron doses (i.e., bi-weekly dosing) starting on Day 1.

Therefore, this study will utilise an open-label design to avoid unnecessary IV placebo injections. This reduces the burden of requiring additional subject visits to both groups (as subjects receiving IS will need more dosing visits than subjects in the FCM group) as well as removing the potential for infection and other side-effects that may result from an IV placebo injection.

IV iron products are designed to deliver, in a controlled way, iron to the body and to replenish iron stores and as a consequence increase Hb concentration. Therefore, the study primary endpoint is the percentage of subjects achieving an increase in Hb \geq 2g/dL (responders) from baseline at any time up to Week 8. Since knowledge of the study drug will not impact this objective parameter, in addition to the fact that all subjects will be receiving IV iron, the open-label design is considered to be the most appropriate design for this study.

2.2 Dose and Drug Selection

Ferric carboxymaltose is an IV iron preparation which, in Europe, is indicated for subjects with ID when oral iron preparations are ineffective or cannot be used. It is a Type 1 iron complex with a low risk of toxicity as Type 1 iron complexes are stable and robust complexes [13]. As such, FCM provides iron for the endogenous iron transport and storage proteins in a controlled manner. This permits FCM to be administered in individual dosing at up to 1,000 mg iron at relatively short time intervals. Moreover, being free of dextran or dextran derivatives, FCM has no risk of dextran-induced immunogenicity. Nevertheless, as with all IV iron preparations, FCM may induce hypersensitivity reactions (see Section 8.1).

The IB summarises data from over 30 completed clinical trials with FCM which supports the administration of doses of up to 1,000 mg per administration, with an approved maximum single dose of 20 mg iron/kg BW.

Traditionally the Ganzoni formula has been used to calculate total iron requirements [9]. However, Evstatiev et al, 2011 [15] have recently demonstrated that FCM dosed using a simplified dosing formula (as proposed in this study) is superior in efficacy to dosing using the Ganzoni formula (using Venofer at multiple 200 mg iron doses). The simplified dosing formula (Table 2) is calculated based on subject BW and Hb. Using this standard formula, the heaviest subjects with low Hb receive the highest cumulative iron doses.

As such, FCM will be administered using this simplified formula for calculating the total iron dose to achieve appropriate repletion of iron requirements.

An IV iron preparation is deemed most appropriate as a comparator arm within this study. Iron Sucrose (Venofer) manufactured by Vifor Pharma is an IV iron preparation available on the Chinese market and was selected as the comparator product. Iron Sucrose has a favourable and well documented safety profile. Alternative products at higher doses are all dextran-based with risk of dextran-induced anaphylactic reactions and other non-dextran based IV irons were less stable than IS and therefore would have required lower maximal single iron doses with an additional visit burden on subjects and participating sites. Additionally, there are numerous studies comparing FCM and IS that confirm the choice as an appropriate comparator. For subjects randomised to the IS arm, dosing (including calculation of the total dose) will be per the approved Chinese label.

2.3 Endpoint and Procedures

2.3.1 Primary Endpoint

As IV iron products are designed to deliver, in a controlled way, iron to the body and to replenish iron stores, and as a consequence increase Hb concentration, the study primary endpoint is the percentage of subjects with an increase in Hb $\geq 2\text{g/dL}$ (responders) from baseline at any time up to Week 8.

The aim is to demonstrate non-inferiority of FCM given in a standardised dosing regimen to the currently approved formulation (IS) given according to the Ganzoni formula with respect to increase in Hb $\geq 2\text{g/dL}$ from baseline at any time up to Week 8. As IS is given in doses of 200 mg iron, it might take longer for the subject to receive the complete iron dose (e.g., 3 weeks with 3 injections per week if 1,800 mg are needed), as compared to FCM. To allow for the control subjects to respond to IV iron treatment, an 8 week study duration is chosen, which is expected to be within 5 weeks after the last treatment received for the majority of the control subjects.

2.3.2 Secondary Endpoints

In addition to demonstrating an increase in Hb ≥ 2 g/dL (responders) from baseline at any time up to Week 8, the study will summarise the absolute and change from baseline of key laboratory parameters, such as Hb, TSAT and serum ferritin as well as the percentage of subjects achieving TSAT ≥ 16 % and serum ferritin ≥ 100 ng/mL (for subjects with underlying inflammation) or serum ferritin > 14 ng/mL (for subjects with no underlying inflammation). This will permit for confirmation of the replenishment of iron stores as well as to document if Hb will increase to values above the normal range and will allow the physician to determine appropriateness of medication.

2.4 Key Inclusion and Exclusion Criteria

The inclusion criteria match the key population where the drug could be utilised. The excluded population reflects known and/or theoretical high-risk populations and/or those with ID due to other causes and are hence excluded from this study.

Due to the wide number of underlying diseases or general population that may suffer from IDA, there are no specific criteria for disease aetiology. However, when including subjects and summarising safety aspects, the underlying disease will be included as a key variable due to the significant impact it may have on serum ferritin levels (inclusion criteria and known to be elevated in subjects with chronic disease) and on the AEs that are reported (as the underlying disease may increase the risk of events including risk of morbidity). Note, all safety events will have physician assessed relationship to study drug recorded to permit distinguishing between events due to disease and those related to drug – with drug related events also presented for the overall population.

Subjects with IDA (defined as Hb < 11 g/dL for females and < 12 g/dL for males, serum ferritin < 100 ng/mL (if subject has concomitant inflammation) or ≤ 14 ng/mL (in non-inflamed subjects), TSAT $< 16\%$, mean corpuscular Hb concentration (MCHC) $< 32\%$, mean corpuscular volume (MCV) < 80 fL, and mean corpuscular Hb (MCH) < 27 pg) will be included. Success of IDA treatment will be assessed by comparing change from baseline in Hb as well as serum ferritin (as marker for iron stores) and TSAT (as marker for circulatory iron pool) between treatment groups. Subjects with hypersensitivity to FCM or any of its excipients, subjects with evidence of iron overload or disturbances in utilisation of iron (i.e. sideroachrestic anaemia) and subjects with anaemia not attributed to ID are excluded as IV iron administration is contraindicated.

3. STUDY OBJECTIVES

3.1 Primary Objective

- To demonstrate the efficacy of FCM given in a simple dosing regimen in correcting IDA, by demonstrating non-inferiority to treatment with the currently approved IV iron therapy of IS (Venofer) in the Chinese population.

3.2 Secondary Objectives

- To assess the safety of FCM compared to IS in the Chinese population.
- To evaluate the effect of FCM compared to IS on relevant laboratory parameters (haematology, chemistry, iron parameters) in the Chinese population.

4. INVESTIGATIONAL PLAN

4.1 Overall Study Design

This is an open-label, randomised controlled study to assess the impact of FCM in correcting IDA compared to Venofer (IS) in Chinese subjects. The study will randomise approximately 368 subjects (184 per group) suffering from different underlying diseases leading to IDA. It is expected that approximately 850 subjects need to be screened to randomise 368 subjects.

After an initial screening period (up to 7 days), eligible subjects will undergo baseline assessments and will be randomised (1:1) to receive either FCM or IS at study Day 1.

In the FCM group, study drug administration will occur on Day 1 and, if needed, on Day 8 and Day 15. Subjects randomised to IS will receive injections/infusions of a maximum of 200 mg iron three times a week until the calculated total iron dose is administered.

All subjects will return for assessment of efficacy and safety at Weeks 2, 4, 6 and 8. The schedule of assessments is provided in Table 1: Schedule of Events.

Randomised subjects who terminate their study participation for any reason regardless of whether the study drug was taken or not, will retain their randomisation number. The next subject will be given the next randomisation number.

The Investigator is responsible for ensuring that consideration is given to the post study care of the subject's medical condition.

4.2 Duration of Subject Participation and Study

The expected duration of subject participation is a maximum of 10 weeks: Screening period duration is up to 1 week; treatment period duration including follow up is 8 weeks (± 4 days).

5. SELECTION AND WITHDRAWAL OF SUBJECTS

5.1 Number of Subjects

Approximately 368 subjects will be randomised into this study. It is expected that approximately 850 subjects will need to be screened to achieve 368 randomised subjects. For detailed justification of the sample size please refer to Section 11.2, Sample Size and Power Calculations.

5.2 Inclusion Criteria

Investigators will be expected to maintain a screening log of all potential study candidates that includes minimum key information about the potential candidate, date, and outcome of the screening process (e.g., enrolled into study, reason for ineligibility, or refused to participate). The following inclusion criteria must be met for each subject:

1. At least 18 years of age.
2. Hb < 11 g/dL (females) or <12 g/dL (males) at screening visit
3. Serum ferritin <100 ng/mL for subjects with underlying inflammatory disease (e.g. IBD, CKD or CHF, as determined by high sensitive C-reactive protein (hsCRP) levels above the normal range) otherwise serum ferritin \leq 14 ng/mL in subjects with no apparent underlying inflammatory disease (as determined by hsCRP levels within normal range) at the screening visit
4. TSAT <16% (any subject) at the screening visit.
5. Microcytic, hypochromic anaemia at the screening visit, defined as:
 - a. MCHC < 32%
 - b. MCV < 80 fL
 - c. MCH < 27 pg
6. Subjects with the ability to understand the requirements of the study and abide by the study restrictions, and who agree to return for the required assessments
7. Before any study-specific procedure is conducted, the appropriate written informed consent must be obtained.

5.3 Exclusion Criteria

1. Subject has known hypersensitivity to any of the products to be administered during dosing.
2. Any history of iron storage diseases such as haemochromatosis.

3. Any history or clinical findings of iron utilisation disorders such as sideroachrestic anaemia
4. Known haemoglobinopathies (e.g. thalassaemia).
5. Any history or clinical findings of anaemia associated with:
 - a. Haematuria
 - b. Vitamin B12 or folic acid deficiency that requires treatment (subjects can be included after deficiency is corrected)
6. Any allergic predispositions, i.e. any history of asthma or atopic allergy. This includes drug allergies.
7. Planned surgery with anticipated blood loss (defined as Hb drop >2 g/dL) in the 3 months post-randomisation.
8. Subject has known malignancy (with or without current treatment), except basal cell or squamous cell carcinoma of the skin or cervical intra-epithelial neoplasia.
9. Haemodialysis (current or planned within the next 3 months).
10. History of IV iron therapy, erythropoiesis stimulating agent (ESA therapy and/or blood transfusion in previous 4 weeks prior to baseline, and oral iron or iron-containing products including Chinese herbal medicines (>75 mg iron/day) in the 7 days prior to baseline.
11. Body weight <35 kg.
12. Chronic liver disease and/or screening ALT or AST above 3 times the upper limit of the normal range.
13. Known human immunodeficiency virus infection, acquired immunodeficiency syndrome, tuberculosis.
14. Known active hepatitis B or C or other active infection (acute or chronic).
15. Subject currently is enrolled in or has not yet completed at least 30 days since ending other investigational device or drug study(ies), or subject is receiving other investigational agent(s).
16. Subject is pregnant or is breast feeding.

17. Female subject of childbearing potential is not using adequate contraceptive methods during the study and for up to 1 month after the last dose of the study medication. Adequate contraceptive methods are defined as those which result in a low failure rate (i.e., less than 1% per year) when used consistently and correctly such as implants, injectables, combined oral contraceptives, some intra-uterine devices, sexual abstinence or vasectomised partner. Non-childbearing potential includes being surgically sterilised at least 6 months prior to the study or post-menopausal, defined as amenorrhoea for at least 12 months.
18. Male subjects planning to father a child within 7 days from the last study drug administration.
19. Subject has any kind of disorder that compromises the ability of the subject to give written informed consent and/or to comply with study procedures and/or other reason(s) that render subject not appropriate for study participation in the opinion of the treating physician.

5.4 Withdrawal of Subjects

5.4.1 Withdrawal of Subjects from Study Drug

Study drug must be stopped if the subject experiences any kind of hypersensitivity reaction related to the study drug during administration. The subject may remain in the study and continue to attend study visits. Whether the subject will receive additional doses of study drug will be discussed with the Medical Monitor and will be decided on a case by case basis.

Subjects may be withdrawn from the study drug if in the opinion of the Medical Monitor or the Investigator there would be a risk to the subject's safety if they received any further dose of study drug. If the subjects are withdrawn from study drug they may remain in the study and continue to attend study visits.

Subjects discontinuing study drug will not be replaced.

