7.2.2 Arm B: Iron Sucrose

For subjects in the individually calculated IS dosage regimen group, the individual iron deficit will be calculated using the formula of Ganzoni [9]:

Cumulative iron deficit [mg] =

$$BW [kg] \times (\text{target Hb}^{(1)} - \text{actual Hb}) [g/dL]^{(2)} \times 2.4^{(3)} + 500 \text{ mg}^{(4)}$$

⁽¹⁾ Target Hb for BW >35 kg = 15 g/dL, respectively 9.3 mmol/L

⁽²⁾ To convert mmol/L to g/dL: multiply Hb (mmol/L) by the factor 1.61145

⁽³⁾ Factor 2.4 = 0.0034 (iron content Hb = 0.34%) x 0.07 (blood volume = 7% of BW) x 10,000 (conversion g/dL to mg/L)

⁽⁴⁾ Iron storage depot

Note: BW = Body weight.

The calculated cumulative IS dose is to be rounded up or down to the nearest 200 mg.

Subjects will receive single doses of IS of up to a maximum single dose of 200mg iron three times a week. Depending on the calculated iron deficit, up to 11 IS injections will be given.

Iron Sucrose (Venofer) will be administered by slow IV push injection at a rate of 1 ml undiluted solution per minute (10 ml of the product in at least 10 minutes; administration time should not exceed 60 minutes) or by drip infusion in a dilution of 1 ml of Venofer in maximum 20 ml 0.9% w/v physiological saline (10 ml of the product in maximum 200 ml saline). Venofer must be used immediately after dilution. The drip infusion rate should be 200 ml solution in at least 30 minutes, and should not exceed 60 minutes.

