7.2.3 IV Administration of Drug (Both Arms)

Study personnel responsible for study drug application will apply a tourniquet, seek a suitable vein, disinfect injection site and perform the vein puncture. It is recommended to use a blue catheter 22 gauge (or pink catheter 20 gauge) and secure it with duct tape. The use of blue butterfly needle is possible.

After the puncture, the correct position of the needle can be reviewed in the vein by flushing with 10 mL NaCl 0.9%. Connect the syringe or infusion set to the needle and slowly inject or infuse the FCM (see Section 7.2.1, Arm A: Ferric Carboxymaltose) or IS (see Section 7.2.2, Arm B: Iron Sucrose). The vein should then be flushed with 5-10 mL saline.

Study medication should only be administered when staff trained to evaluate and manage anaphylactic reactions are immediately available, in an environment where full resuscitation facilities can be assured. Each subject should be observed for adverse effects during and for at least 30 minutes following each injection. Hospitalisation for study drug administration is not a requirement of the study. However, Investigators might choose to hospitalise subjects while they receive study drug as a precautionary measure. Hospitalisation for this purpose does not fulfil the criteria of a serious adverse event (SAE) and will not be recorded as such. If an AE/SAE occurs before, during or after administration of study drug during

hospitalisation, this shall be assessed and recorded as per seriousness criteria for AE/SAEs.

Since FCM has a physiological pH, pain at the injection site is very unlikely, therefore caution should be given to avoid paravenous injections. The choice of an appropriate needle for the IV access should minimise the potential risk of a paravenous injection of FCM or IS. Iron Sucrose has a basic pH and therefore, if paravenous leakage occurs, a burning sensation is felt by the subject.

Treatment administration of FCM or IS must be discontinued immediately if swelling (paravenous injection) is observed, which can cause irritation and a brown discolouration of the skin which can be long-lasting. No rinsing or pressure bandage should be used, in order to prevent distribution and extension of extravasations. Study treatment can be re-administered in a different location (i.e. other arm).

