8. RISKS/PRECAUTIONS

8.1 IV irons

Parenterally administered iron preparations can cause hypersensitivity reactions including anaphylactoid reactions, which may be fatal. Therefore, facilities for cardiopulmonary resuscitation must be available. If allergic reactions or signs of intolerance occur during administration, the treatment must be stopped immediately. Hypersensitivity reactions have also been reported after previously uneventful doses of any parenteral iron complexes, including FCM and IS. Each subject should be observed for adverse effects during and for at least 30 minutes following each study drug (FCM or IS) application.

In subjects with liver dysfunction, parenteral iron should only be administered after careful benefit/risk assessment. Parenteral iron administration should be avoided in subjects with hepatic dysfunction where iron overload is a precipitating factor, in particular porphyria cutanea tarda. Careful monitoring of iron status is recommended to avoid iron overload.

Parenteral iron must be used with caution in cases of acute or chronic infection, asthma, eczema or atopic allergies. It is recommended that the administration of FCM or Venofer be stopped in subjects with ongoing bacteraemia. In subjects with chronic infection, a benefit/risk evaluation has to be performed, taking into account the suppression of erythropoiesis (due to chronic infection).

Paravenous leakage must be avoided because leakage of FCM or IS solution at the injection/infusion site may lead to irritation of the skin and potentially long-lasting, brown discolouration at the site of injection/infusion. In the event of paravenous leakage, administration of FCM or IS must be stopped immediately. Study treatment may be re-administered in a different location (i.e. other arm), but extra care needs to be taken to make sure that paravenous leakage does not occur again. This also needs to be clearly documented in the CRF and the source data. If a subject did not receive the full dose, this also needs to be recorded.

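### The stop-and-consult rule for hypersensitivity covers only reactions during administration and sets no severity limit on re-dosing

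*Protocol*

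**What the plan says.** Protocol Section 5.4.1 opens with the mandatory rule: "Study drug must be stopped if the subject experiences any kind of hypersensitivity reaction related to the study drug during administration". The subject may stay in the study. On later doses it continues: "Whether the subject will receive additional doses of study drug will be discussed with the Medical Monitor", with the decision made case by case. A second paragraph lets the Medical Monitor or the Investigator take a subject off study drug if a further dose would be a safety risk. That paragraph is permissive and gives no criteria.

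Section 7.2.3 sets the monitoring period: "Each subject should be observed for adverse effects during and for at least 30 minutes following each injection". Section 8.1 repeats it and states the hazard: "Parenterally administered iron preparations can cause hypersensitivity reactions including anaphylactoid reactions, which may be fatal". The stop instruction in Section 8.1 is also limited to reactions during administration.

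On entry, Exclusion 1 (Section 5.3) bars a subject where "Subject has known hypersensitivity to any of the products to be administered during dosing". Section 2.4 names "Subjects with hypersensitivity to FCM or any of its excipients" at the head of a list that ends "subjects with anaemia not attributed to ID are excluded as IV iron administration is contraindicated".

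On the number of iron sucrose (IS) doses, Section 7.2.2 says: "Depending on the calculated iron deficit, up to 11 IS injections will be given".

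**The concern.** The protocol asks staff to watch every subject for at least half an hour after each dose because hypersensitivity is the main acute danger of both products. Yet the one rule that requires contact with the Medical Monitor before further dosing is tied to a reaction seen while the drug is running. A reaction ten minutes after the infusion ends is the kind of event the observation period exists to catch, and it does not trigger that rule.

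The rule also treats all related reactions alike. A mild flush and an anaphylactoid reaction lead to the same case-by-case discussion, and nothing in the text rules out another dose after either. The entry criteria reflect a more cautious view: known hypersensitivity to the product is reason enough not to give it.

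What is at stake is the safety of a small number of subjects, with a serious possible consequence for each. The primary efficacy comparison is not at stake.

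**Working it through.** **Which provisions reach which reaction.** The plan states no figure on this point, so the first check is to read the relevant sections side by side.

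| Provision | During administration | After the dose, before the next | Bars a further dose? |
|---|---|---|---|
| Protocol 5.4.1, first paragraph | Mandatory stop; discussion with Medical Monitor | Not covered | No, case by case at any severity |
| Protocol 5.4.1, second paragraph | Optional | Optional | Only by judgement |
| Protocol 5.4.2 (AEs judged unacceptable; subject's best interest; interfering condition) | By judgement | By judgement | Only by judgement; hypersensitivity not named |
| Protocol 7.7 | Treatment of the reaction | Treatment of the reaction | Silent |
| Protocol 8.1 | Mandatory stop | Observation only | Silent |
| SAP Appendix 1, Study Drug Deviation #3 | Failure to stop is Major | Not covered | Silent |

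A post-dose reaction therefore reaches only discretionary provisions, and no row sets a severity at which dosing must end. The protocol does write firm rules for other events: Section 7.6 discontinues a subject with Hb below 6 g/dL, and Section 5.4.2 does so for pregnancy and transfusion.

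**How many doses remain after a first-dose reaction.**

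- FCM (Table 2 and its note): 1, 2 or 3 planned doses, so 0, 1 or 2 remain. Doses are 7 days apart.
- IS, the 65 kg, Hb 9 g/dL subject of Section 2.1: 65 × (15 − 9) × 2.4 + 500 = 1,436 mg, which reproduces the protocol's figure. Rounded to 1,400 mg this is 7 doses, so 6 remain.
- IS at the maximum in Section 7.2.2: 11 doses, so 10 remain. The table in SAP 4.5 lists 400 mg as possible by Day 2, so the next dose can fall on the following day.

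**How often.** No hypersensitivity rate is given. The nearest figure is Section 1.2.4: 1.7% of subjects had severe TEAEs of any kind. Applied to the 184 FCM subjects, 0.017 × 184 = 3.1. That covers all causes, so it serves only as a rough ceiling for severe reactions in that arm.

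**What a permanent stop would do to the primary analysis.** A subject who stays in the study but stops early can fall below the 80% compliance needed for the PPS (SAP 3.3 and 4.5). For example, one 1,000 mg FCM dose of a planned 1,500 mg is 66.7%, and one IS dose of seven is 14.3%.

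Inputs: 147 per arm and a 70% response in both arms (Protocol 11.2), and 0.70 × 147 = 102.9, taken as 103 responders. The method is that of SAP 4.6.1, with *l* and *u* the continuity-corrected Wilson limits and *z* = 1.96:

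lower bound = (p₁ − p₂) − √[(p₁ − l₁)² + (u₂ − p₂)²]

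Base case: p₁ = p₂ = 0.7007, l₁ = 0.6188, u₂ = 0.7719. The bound is 0 − √(0.0819² + 0.0712²) = −10.86%.

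| Subjects leaving the PPS | 1 | 2 | 3 |
|---|---|---|---|
| FCM non-responders | −10.38% | −9.90% | −9.42% |
| IS non-responders | −11.32% | −11.79% | −12.27% |
| Non-responders, this many from each arm | −10.85% | −10.84% | −10.83% |
| FCM responders | −11.09% | −11.33% | −11.57% |

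Every bound is above −15%. FAS membership does not depend on compliance, so it is unchanged.

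**The case against.** The strongest reply is that the protocol already has a working safeguard. For a reaction during dosing, the drug is stopped and further doses are discussed with the Medical Monitor. Re-dosing is permitted, not required. For a later reaction, the second paragraph of 5.4.1 and the items in 5.4.2 are not limited to the administration period, so an attentive investigator has all the authority needed. Once a dose has finished there is nothing left to stop; only the consultation is missing. Exclusion 6 also keeps out subjects with asthma, atopy or drug allergy, and hypersensitivity is not among the FCM reactions that Section 8.2 lists at 1% to 10%. The Investigator's Brochure and the Chinese product insert, which are not part of these documents, may state contraindications.

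Much of this stands, and it limits the point to a gap in a rule, not an absence of protection. It does not remove the gap. Discretion without criteria is weaker than the mandatory step already written for reactions during dosing, and 5.4.1 does not tie the re-dosing decision to the Brochure or the insert.

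A reader might infer three stronger things that the documents do not support:

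- **That 5.4.1 contradicts 2.4 and Exclusion 1.** Those texts govern entry, while 5.4.1 governs treated subjects. Section 2.4 names only FCM and its excipients, so for IS the comparison rests on Exclusion 1 alone. Re-dosing after a mild reaction is also a defensible choice.
- **That the size of the gap can be read from the clock.** Thirty minutes after a short injection is most of the observed time, but share of time is not share of risk, and the documents do not say when reactions occur.
- **That re-dosing a severe reactor is likely.** An assumed reaction rate would give the chance of a reaction, not the chance that the Medical Monitor and Investigator then agree to dose again.

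The larger number of remaining IS doses is a feature of the two regimens. It shows where re-exposure could occur and is not evidence of bias in the safety comparison.

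**Conclusion.** The point holds as a cheap safety improvement. Followed as written, the protocol requires no consultation after a hypersensitivity reaction in the observation period or before the next dose, and it leaves further doses open after an anaphylactoid, serious or severe related reaction. The opportunity for re-exposure is 0 to 2 doses in the FCM arm; in the IS arm it is 6 in the protocol's own example and 10 at most. Its frequency cannot be estimated from the documents.

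The primary efficacy conclusion is unaffected. The bounds assume 147 per arm, 70% response in both arms, and 1 to 3 subjects leaving the PPS.

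**What to change.** Replace the first paragraph of Protocol 5.4.1, for both arms, with text to this effect:

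> If a subject has a related hypersensitivity reaction during administration, in the observation period of at least 30 minutes, or at any time before the next dose, any ongoing administration is stopped and no further dose is given until the Medical Monitor has been consulted and the decision recorded. Study drug ends permanently if the reaction is anaphylactic or anaphylactoid, serious (Section 10.1.5) or severe (Section 10.2.1). Other reactions are decided case by case. Subjects taken off study drug may stay in the study for the remaining visits.

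No change to SAP Appendix 1 is essential. Its item on subjects not withdrawn as per protocol names Hb below 6 g/dL only as an example, so it can be read to cover a breach of the new rule. Widening Study Drug Deviation #3 to match would do no harm. The PPS definition can stay as it is.

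The cost is one amended paragraph and the site training that goes with it. No new CRF field is needed: Section 10.3.1 already collects onset time on dosing days, intensity, seriousness and relationship. The trade-off is that a few subjects receive less iron and may leave the PPS, with the negligible effect on the bound shown above.
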